5.8.4. Vital Signs

Vital signs parameters include weight (kg), heart rate, systolic and diastolic blood pressure, respiratory rate, and temperature ($^{\circ}\text{C}$). Vital signs are recorded at Screening and on Days 1, 8 and 15 of each cycle. For each parameter at each time point, the observed values and change from baseline will be summarized by dose cohort. Vital sign data will also be listed for all patients.

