#### 7.4. Potential Risks of Human Use

Increases in hematologic parameters (RBC, hemoglobin, hematocrit, reticulocytes) are expected pharmacologic effects of ACE-536 treatment. Increases in systolic and diastolic blood pressures may occur in concert with increases in hemoglobin values. Excessive or rapid increases in hemoglobin or blood pressure may occur and will be monitored. Dose modifications rules for individual subjects and dose escalation/reduction rules will be utilized to minimize risks associated with increased RBC parameters.

Adverse events observed in the Phase 1 study in healthy volunteers that were considered probably or possibly related to study drug included injection site hemorrhage, injection site macule, and dry skin, hyperesthesia, muscle spasms, myalgia, generalized pruritis, and papular rash.

Membranoproliferative glomerulonephritis was observed in both rats and monkeys, likely secondary to immune complex deposition. These findings were associated with increases in serum BUN and creatinine. The presence of immune complexes in renal tissue from monkeys treated with ACE-536 was demonstrated by immunohistochemistry.

The growth of heart and lungs was slightly reduced in rats exposed to ACE-536 as compared with control animals; these decreased heart and lung weights were reversible and there was no

corresponding histology finding. These findings were not replicated in the monkey toxicology studies; the potential for these adverse effects in humans is unknown.

Based on rat toxicology studies, treatment with ACE-536 may affect the adrenal gland. These findings were specific to the rat as they were not replicated in the monkey toxicology studies.

As with all biologics, there is the potential for anti-drug antibodies that can be associated with increased drug clearance and hypersensitivity reactions. Anti-drug antibody formation against ACE-536 as well as human ActRIIB protein will be monitored in the initial clinical studies.

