## 9.2. Discussion of Study Design

The efficacy assessment based on modified IWG criteria for erythroid response (mHI-E) was selected for this study as a variation of the accepted and widely used endpoint for the evaluation of therapies in patients with MDS, appropriate for short-term studies. This was selected as the primary endpoint due to the unknown optimal dosing interval for ACE-536 to produce a sustained response and the desire to identify the minimal safe dose level producing any erythroid response. The standard HI-E criteria for response will be evaluated as a secondary endpoint.

The initial dose level of 0.125 mg/kg is less than the maximum dose administered in the phase 1 study A536-02 of 0.25 mg/kg, which was safe and well tolerated, and produced a hemoglobin response in healthy volunteers. The safety measurements are standard for studies with investigational medications. An open-label study, conducted in a limited number of patients, with protocol-specified definitions of dose-limiting toxicity, and with protocol-specified procedures for dose escalation and reduction is considered appropriate for a proof-of-concept study in this target patient population. Dose escalation in sequential cohorts is designed to minimize the risk of excessive erythroid response and hypertension that may result from a robust response to high drug levels. Individualization of dose level in the expansion cohorts, using dose titration rules based on hemoglobin response and dose reduction rules based on safety information will maximize the proportion of patients having an erythroid response while maintaining safety.

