## 14. ASSESSMENT OF SAFETY

### 14.1. Adverse Event Definitions

#### Adverse Event

An adverse event (AE) is any untoward medical occurrence in a patient or clinical investigation subject administered a study drug, which does not necessarily have a causal relationship with this treatment. An AE can therefore be any unfavorable and unintended sign (including an abnormal laboratory finding), symptom, or disease temporally associated with the use of the study drug whether or not it is considered related to the study drug.

Abnormal laboratory and other abnormal investigational findings (e.g. physical exam, ECG) should not be reported as AEs unless they are associated with clinical signs and symptoms, lead to treatment discontinuation or are otherwise considered clinically relevant by the investigator. In cases of surgical or diagnostic procedures, the condition/illness leading to such a procedure is considered as the AE rather than the procedure itself. In case of a fatality, the cause of death is considered as the AE, and the death is considered as its outcome.

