### 15.2.3. Secondary Analysis

**Safety analysis:** To assess clinical safety, adverse events, vital sign measurements and clinical laboratory information will be summarized. Adverse Events will be coded using the Medical Dictionary for Regulatory Activities (MedDRA). Changes from baseline for clinical laboratory values and vital signs will be summarized over time. Descriptive statistics and shift tables will be generated as appropriate.

**Secondary efficacy/pharmacodynamic analysis** of the study will be performed using the ITT and EE populations and will include:

- Modified erythroid response (mHI-E), as described above for primary endpoint, performed using the ITT population.
- HI-E response rate as defined by IWG 2006 criteria ([Appendix 5](#)). Improvements must last  $\geq$  8 weeks. For non-transfusion dependent patients, an increase of  $\geq 1.5$  g/dL from pre-treatment hemoglobin. For transfused patients, a reduction by  $\geq 4$  units of RBCs transfused (for a hemoglobin  $\leq 9.0$  g/dL) during any 8-week period on study, compared with the 8-week period prior to Cycle 1 Day 1.
- Time to mHI-E and HI-E response and duration of mHI-E and HI-E response as per the IWG 2006 criteria.
- Frequency of RBC transfusion, and rate of RBC transfusion independence in transfusion dependent patients.
- Other pharmacodynamic (PD) endpoints including:
  - Biomarkers for iron metabolism
  - Biomarkers for bone metabolism
  - Relationship of biomarkers to response
  - Rates of HI-N and HI-P

**Exploratory endpoints** will include:

- Evaluation of biomarkers related to the TGF $\beta$  superfamily.
- Evaluation of self-reported quality of life in the expansion cohort using tools including but not limited to the FACT-An questionnaire.

All binary endpoints will be summarized using both a point estimate and its exact confidence interval based on the binomial distribution. The time-to-event type secondary endpoints will be analyzed using Kaplan-Meier method to estimate the survival curve and median time to event and 95% confidence interval.

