#### **15.2.4. Pharmacokinetics Analysis**

**Pharmacokinetics analysis:** Non-compartmental PK parameters for ACE-536, such as maximum plasma concentration ( $C_{max}$ ), time to maximum plasma concentration ( $t_{max}$ ), and area under the concentration/time curve (AUC), will be estimated. Dose proportionality may be assessed using the exposure data (e.g.  $C_{max}$ , AUC) after the first dose if sufficient dose levels are studied. Descriptive statistics will be provided for serum concentrations and PK parameters. The relationship between ACE-536 exposure and response (i.e., safety, efficacy, and biomarkers) may be explored, if appropriate.

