5.8.2. Adverse Events

All AEs and SAEs occurring after the Cycle 1 Day 1 dose through 56 days after the last study drug administration are to be reported and documented on the AE CRF.

Treatment emergent adverse events (TEAE) are defined as

1. AE starting or worsening after the first date of study drug;
2. AE occurs on the first date of study drug and the onset check box is marked “Onset after first dose of study drug”;
3. AE with a missing start date and a non-missing stop date on or after the first dose of study drug;
4. AE with both a missing start and stop date.

A drug-related TEAE is defined as any TEAE related to the study medication as assessed by the investigator or with missing assessment of the causal relationship.

The following summaries will also be presented:

- Number and percentage of patients reporting each AE, categorized by System Organ Class (SOC) and Preferred Terms (PT)
- Number and percentage of patients reporting each AE experienced by $\geq 5\%$ and $\geq 10\%$ of patients in all patients by PT
- Number and percentage of patients reporting SAE, categorized by System Organ Class (SOC) and Preferred Terms (PT)
- Number and percentage of patients reporting Grade ≥ 3 AE, categorized by System Organ Class (SOC) and Preferred Terms (PT)
- Number and percentage of patients reporting related AE, categorized by System Organ Class (SOC) and Preferred Terms (PT)
- Number and percentage of patients reporting AE leading to drug withdrawal, categorized by System Organ Class (SOC) and Preferred Terms (PT)
- Number and percentage of AE of interests by cycle: AE of interests include new malignancy and premalignant lesions (excluding benign tumors or benign neoplasia)

Note that counting will be by patient, not event, and patients are only counted once within each SOC or preferred term. If a patient experiences the same AE at more than one severity, or with more than one relationship to study drug, the most severe rating or the stronger causal relationship to study drug will be given precedence. Any missing severity, causality, or outcome will not be imputed and classed as unknown.

All AEs will be listed. The following listings will also be provided: 1) patients with SAEs; 2) patients with Grade ≥ 3 AEs; and 3) patients with AEs leading to discontinuation.

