5.10. Exposure/Response Analysis

The relationship between ACE-536 exposure and Hb and RBC units will be explored.

The exposure endpoint will be AUC for the starting dose. The erythroid response endpoints will include the following depending on study population.

- Patients who are transfusion-free on treatment:
 - Mean of change from baseline in Hb in Week 1-3 (average of weekly Hb measures from Day 7 to 21). This measure represents the initial rate of Hb increase. Patients who receive at least 1 luspatercept dose will be included.
 - Mean of change from baseline in Hb in Week 1-15 (average of weekly Hb measures from Day 7 to 105). Patients who receive at least 3 luspatercept doses will be included.
- Patients with high transfusion burden (requiring ≥ 4 RBC units in 8 weeks at baseline): Change from baseline in RBC units transfused in Week 1-15. Patients who received at least 3 luspatercept doses will be included.

Change in Hb level or RBC unit will be plotted as a function of luspatercept AUC. Linear or nonlinear function may be used to describe the relationship. The relationship may be stratified by baseline EPO levels.

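### Blood pressure rise is a named risk, but no planned table counts the patients with a marked measured rise (SAP 5.8.4): a modest reporting gap

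*SAP*

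**What the plan says.** **The risk.** Protocol 7.4 states: "Increases in systolic and diastolic blood pressures may occur in concert with increases in hemoglobin values". It adds that excessive or rapid rises will be monitored. Protocol 9.2 explains that escalating in sequential cohorts is meant to "minimize the risk of excessive erythroid response and hypertension that may result from a robust response to high drug levels".

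**The planned output for measured BP.** SAP 5.8.4 treats systolic and diastolic BP like weight or temperature: "For each parameter at each time point, the observed values and change from baseline will be summarized by dose cohort". A listing of all patients accompanies this. SAP 5.2 fixes the statistics as n, mean, standard deviation, minimum, median and maximum. Under SAP 5.14.4, several readings in one visit window are averaged. By contrast, laboratory values get a shift table from baseline to end of treatment (SAP 5.8.3), and ECG interpretation gets improvement and deterioration categories (SAP 5.8.5).

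**Neighbouring provisions.**
- Protocol 15.2.3, after naming laboratory values and vital signs, says: "Descriptive statistics and shift tables will be generated as appropriate". SAP 5.8.4 specifies none for vital signs.
- Protocol 15.2.4 says the relationship between exposure and "response (i.e., safety, efficacy, and biomarkers) may be explored, if appropriate". SAP 5.10 narrows this: "The relationship between ACE-536 exposure and Hb and RBC units will be explored".
- In the adverse event (AE) tables of SAP 5.8.2, "counting will be by patient, not event, and patients are only counted once within each SOC or preferred term". Protocol 14.1 says abnormal investigational findings "should not be reported as AEs unless they are associated with clinical signs and symptoms", lead to discontinuation, or are otherwise judged clinically relevant by the investigator.
- Under protocol 10.7 the SRT reviews vital signs and erythroid response data in both the escalation and expansion phases.

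**The concern.** The risk in protocol 7.4 and 9.2 concerns individual patients: someone whose hemoglobin rises strongly may become hypertensive. The natural questions for the study report are how many patients had a marked rise in measured BP, and whether they were the patients whose hemoglobin rose. A cohort mean at each visit answers neither, because a few large rises barely move it. The by-visit maximum shows how large the biggest rise was, but not whether it belongs to the same patient each time.

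This matters mainly in the expansion cohorts of about 25 to 30 patients. In escalation cohorts of 3 to 6, the minimum, median, maximum and listing come close to showing the data. For the expansion cohorts a reader would have to rebuild the count from the listing, which could hold up to (30 + 56 + 9) × 15 = 1,425 post-baseline BP pairs. That bound mixes planned maxima for cohorts 1 and 2 with the 9 patients actually treated in cohort 3.

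**Working it through.** The documents give no figure to reproduce here. The check asks whether the planned tables determine the patient count, and then how a worst-value table would behave.

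**Inputs from the documents.** Statistics per visit: SAP 5.2. Cohort size 30: SAP 3.1, expansion cohort 1. Post-baseline visits: Days 8 and 15 of cycle 1, Days 1, 8 and 15 of cycles 2 to 5, and end of treatment, so 2 + 12 + 1 = 15. Limits of 150 systolic and 100 diastolic: protocol 9.3.2, exclusion 11. Baseline BP is the last observation on or before Cycle 1 Day 1: SAP 5.1. All BP values and standard deviations below are assumptions.

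**Step 1: do the by-visit tables fix the count?** Take 30 patients, each with baseline 130, and at every visit one reading of 155 and 29 of 130.
- Mean = 130 + 25/30 = 130.8; SD = 25/√30 = 4.6; minimum and median 130; maximum 155.
- Pattern A: the same patient is high at all 15 visits. Patients ever at 155: 1/30 = 3%.
- Pattern B: a different patient is high at each visit. Patients ever at 155: 15/30 = 50%.

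Every observed-value and change table is the same in A and B. The reason is general: these statistics do not alter when patients are relabelled within a visit. A second constructed case (30 patients, 14 visits, two rises of at least 20 mm Hg per visit) gave identical tables (mean change 1.95, SD 9.06, maximum 27) with anywhere from 2 to 28 of 30 patients affected.

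**Step 2: window averaging.** With baseline 140 and readings of 165 and 145 in one window, the analysed change is (165 + 145)/2 − 140 = 15, against a peak change of 165 − 140 = 25.

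**Step 3: noise in a threshold count.** Assume independent readings with visit SD 8 to 10 mm Hg. For an unaffected patient with true systolic BP μ, P(any of 15 readings ≥ 150) = 1 − Φ((150 − μ)/SD)^15. For a sustained +25 over the last 8 visits, it is 1 − Φ((150 − μ)/SD)^7 × Φ((125 − μ)/SD)^8.

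| True systolic BP | Unaffected | Sustained +25 |
|---|---|---|
| 115 | under 1% | 59–75% |
| 120 | 0.1–2% | 92–95% |
| 130 | 9–29% | over 99% |
| 140 | 81–93% | over 99% |

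A real table would be split by observed baseline. If true systolic BP has mean 130 and SD 10, and visit SD is 10, unaffected patients reach 150 in 20%, 48% and 69% of cases for observed baseline <130, 130–139 and 140–149.

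**Step 4: maximum change from baseline.** For unaffected patients the mean maximum change is 13.9 to 17.3 mm Hg with 15 readings, but 6.8 to 8.5 with 3. At a fixed true BP it correlates about −0.88 with the single baseline reading, so about 0.88² = 77% of its variance is baseline noise. Under the Step 3 assumptions with visit SD 10, its mean in unaffected patients is about 23, 15 and 10 mm Hg across the three observed-baseline strata.

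**Step 5: a plot of maximum BP change against maximum hemoglobin increase.** The Fisher-z 95% interval around zero correlation is ± tanh(1.96/√(n − 3)): ±0.395 at n = 25 and ±0.360 at n = 30. If 10–30% of patients stop after 3 visits, both maxima shrink together. That alone gives a correlation of about 0.06–0.13 (assumed hemoglobin visit SD 0.5 g/dL).

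**The case against.** The strongest reply is that nothing promised is missing. Protocol 15.2.3 commits to summarizing vital-sign changes over time, and SAP 5.8.4 does so. Shift tables are promised only where appropriate, and SAP 5.2 makes every summary descriptive. The risk is also handled elsewhere. The SRT sees vital signs alongside erythroid data. Protocol 14.5 requires clinically relevant changes in clinical findings to be recorded as AEs, protocol 14.3 has them graded by CTCAE, and SAP 5.8.2 counts patients by preferred term, Grade ≥3, relatedness and withdrawal. What escapes is a rise without symptoms or discontinuation that the investigator judged not clinically relevant. The limits of 150 and 100 are entry criteria, not on-treatment safety thresholds. Steps 3 and 4 show that worst values are noisy.

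Most of this stands, and it limits the point to a modest one. It does not remove it. AE counts depend on investigator judgement in an open-label study, SRT review is not a report table, and the report would still not give the number of patients with a marked measured rise.

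A reader might also infer that maximum change avoids the threshold's dependence on starting level. Step 4 shows that it does not: with one observed baseline reading, unaffected patients with low baselines show the largest changes.

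**Conclusion.** The gap is real and modest. The planned tables of measured BP cannot say how many patients had a marked rise; in the example, 3% and 50% give the same output. That conclusion follows from the form of the statistics and needs no assumption about BP variability. The figures on how a fix would perform do rest on assumed SDs and independent readings.

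Three stronger readings are not supported:
- **That the plan breaks a commitment.** The protocol wording on shift tables and on exposure–safety analysis is permissive.
- **That individual BP results go unreported.** The listing gives every patient's values, and by-visit maxima show the largest rises. What is missing is a tabulated patient count.
- **That BP safety is unmonitored.** AE recording and SRT review cover the rises judged to matter clinically.

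One caveat: the SAP follows protocol amendment 06 and includes expansion cohort 3. The supplied protocol does not, so its BP text may come from an earlier version.

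**What to change.** Add to SAP 5.8.4 one descriptive shift table of baseline against worst individual post-baseline BP, using single readings and not window averages. Suitable categories are systolic <130, 130–139, 140–149 and ≥150, and diastolic <90, 90–99 and ≥100. State the number (%) of patients reaching ≥150 systolic or ≥100 diastolic. Present it for each expansion cohort and for the pooled lower-dose and higher-dose groups of SAP 5.7. Leave the escalation cohorts of 3 to 6 to the listing, since splitting them by baseline would give near-empty cells.

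Optionally, plot each patient's maximum BP change against maximum hemoglobin increase, excluding hemoglobin within 7 days after transfusion. SAP 5.7.2.9 already derives that increase for low transfusion burden patients; high transfusion burden patients would need it added.

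The cost is a few lines of SAP text, one table and perhaps one plot, with no new data. A footnote should state the limits: there is no control group, threshold crossings and maxima include measurement noise and grow with the number of readings, early discontinuation lowers them, and maximum change is subject to strong regression to the mean because baseline is a single reading.

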5.8.5. ECG Results

12 lead ECG results are recorded at Screening, Cycle 2 Day 1, and at the end of treatment visit. The quantitative ECG assessments (Ventricular rate, QRS width, PR interval, QTcF, interval) will be summarized at each time point by dose cohort.

ECG overall interpretation (normal, abnormal not clinically significant and abnormal clinically significant) will be presented for actual values and changes from baseline (Screening observation) to each post baseline visit [expressed as Improvement, No Change, and Deterioration] by dose cohort.

Note:

- Improvement = Abnormal Clinically Significant (CS) to Abnormal Not Clinically Significant (NCS)/Normal, Abnormal NCS to Normal
- Deterioration = Normal to Abnormal NCS/CS, Abnormal NCS to Abnormal CS
- No change = Normal to Normal, Abnormal NCS to Abnormal NCS, Abnormal CS to Abnormal CS

If either result is missing for any patient, then an 'Unknown' category will be presented.

ECG results will be listed for all patients.

5.8.6. Physical Examination

A physical examination is conducted at Screening and on Day 1 of each cycle and at the end of treatment and end of study visits. Physical exam details will be listed only.

5.9. Pharmacokinetics Analysis

5.9.1. Pharmacokinetic Sampling Schedule

Blood samples for determination of ACE-536 serum concentrations are collected from all patients at the following schedule:

Treatment/Follow Up	Visit	Study Day	PK Sample
Dose 1	Cycle 1 Day 1	1	X
	Cycle 1 Day 8	8	X
	Cycle 1 Day 11	11	X
	Cycle 1 Day 15	15	X
Dose 2	Cycle 2 Day 1	22	X
	Cycle 2 Day 8	29	X
Dose 4	Cycle 4 Day 1	64	X
Dose 5 (Final Dose)	Cycle 5 Day 1	85	X
	Cycle 5 Day 8	92	X
	Cycle 5 Day 15	99	X
Follow up Period	End of Treatment	113	X
	Post-Treatment Follow Up	141	X
	End of Study	169	X

Acceptable time windows for pharmacokinetic blood draws are \pm 1 day in Cycle 1, \pm 2 days in Cycles 2 to 5, and \pm 7 days in the follow-up period.

5.9.2. Data Handling

Concentrations that are below the limit of quantitation (BLQ) prior to the first dose will be assigned a numerical value of zero. Post-treatment concentrations that are BLQ will be treated as missing.

Concentrations assigned a value of missing will be omitted from the descriptive statistics. A concentration value of zero will be excluded from the computation of the geometric mean (geometric CV%). If any patients are found to be noncompliant with respect to dosing, have incomplete data, or encounter other circumstances that would affect the evaluation of pharmacokinetics, a decision will be made on a case-by-case basis as to their inclusion in the pharmacokinetic analyses. Data excluded from pharmacokinetic analysis will be included in the data listings, but not in the summaries.

In tables and listings for the derived pharmacokinetic data, there should be four decimal places for numerical values below 1, three decimal places for numeric values below 10 but above 1, and two decimal places for numeric values above 10. However, the listings of raw data should not have more decimal places than the actual data.

